6.3 Lifestyle Restrictions

There are no lifestyle restrictions applicable for this study given that the participants will receive the study investigational products (IPs) intravenously.

6.4 Screen Failures

Screen failures are defined as participants who consent to participate in the clinical study but are not subsequently randomized/entered in the study/included in the analysis population. A minimal set of screen failure information is required to ensure transparent reporting of screen failure

participants, to meet the Consolidated Standards of Reporting Trials (CONSORT) publishing requirements (see Appendix 8), and to respond to queries from regulatory authorities. Minimal information includes date of consent, demography, screen failure details, eligibility criteria, and any SAEs.

6.4.1 Retesting During Screening

This study permits the re-enrollment of a participant who has discontinued the study as a pretreatment failure (ie, participant has not been randomized/has not been treated). If re-enrolled, the participant must be re-consented.

Retesting of laboratory parameters and/or other assessments within any single screening period will be permitted (in addition to any parameters that require a confirmatory value).

The most current result prior to randomization is the value by which study inclusion will be assessed because it represents the participant's most current, clinical state.

Laboratory parameters and/or assessments that are included in Table 2-1 may be repeated in an effort to find all possible well-qualified participants. Consultation with the BMS Medical Monitor/Study Director (or designee) may be needed to identify whether repeat testing of any particular parameter is clinically relevant.

7 TREATMENT

Study treatment is defined as any investigational treatment(s) or marketed product(s) intended to be administered to a study participant according to the study randomization or treatment allocation.

Study treatment includes IPs/investigational medicinal products (IMPs) and non-IPs/IMPs and can consist of the following:

- BMS-986226
- Nivolumab
- Ipilimumab
- Tetanus Vaccine

An IP, also known as IMP in some regions, is defined as a pharmaceutical form of an active substance or placebo being tested or used as a reference in a clinical study, including products already with a marketing authorization but used or assembled (formulated or packaged) differently from the authorized form, used for an unauthorized indication, or when used to gain further information about the authorized form.

Other medications used as support or escape medication for preventative, diagnostic, or therapeutic reasons, as components of the standard of care for a given diagnosis, may be considered as non-IPs.

Product Description / Dosage Form	Potency	IP/NonIMP	Blinded or Open Label	Packaging / Appearance	Storage Conditions (per Label)
BMS-986226-01 Solution for Injection	10 mg/mL	IP	Open	Vial	2 to 8 °C, Protect from light
Nivolumab Solution for Injection	10 mg/mL	IP	Open	Vial	2 to 8 °C, Protect from light and freezing
Ipilimumab Solution for Injection	5 mg/mL	IP	Open	Vial	2 to 8 °C, Protect from light and freezing
Tetanus vaccine	Per local ^a	IP	Open	Various packaging configuration	Refer to the label on container and/or pharmacy manual

Abbreviations: IP = investigational product

^a Tetanus vaccine (Tdap preferred, Td or equivalent after discussion with the Medical Monitor/Study Director or designee) will be obtained as local commercial product in countries if allowed by local regulations or through investigating sites standard prescribing procedures.

7.1 Treatments Administered

The selection and timing of dose for each participant are presented in Table 7.1-1.

Table 7.1-1:Selection and Timing of Dose per Part

Study Treatment	Dose Level	Frequency of Administration	Route of Administration	Infusion time (Minute)
Preliminary Safety (Cohorts and Part A			
BMS-986226	2, 8, 25, 80, 200, 400, 800 mg	Q4W	IV	30
Part B1				
Nivolumab	480 mg	Q4W		30
BMS-986226	3 Doses evaluated by BLRM-copula, PK/PD	Q12W	IV	30
Part B2				
Nivolumab	480 mg	Q4W	IV	30
BMS-986226	3 Doses evaluated by BLRM-copula, PK/PD	Q4W	IV	30
Part C1				
Ipilimumab	3 mg/kg ^a	Q4W		30
BMS-986226	3 Doses evaluated by BLRM-copula, PK/PD	Q12W	IV	30

Revised Protocol No.: 04 Date: 31-May-2019

Study Treatment	Dose Level	Frequency of Administration	Route of Administration	Infusion time (Minute)
Part C2				
Ipilimumab	3 mg/kg ^a	Q4W		30
BMS-986226	3 Doses evaluated by BLRM-copula, PK/PD	Q4W	IV	30
Part D				
Nivolumab	480 mg	Q4W	IV	30
BMS-986226	PK/PD from Part B	TBD	1 V	30
Part E				
Ipilimumab	3 mg/kg ^a	Q4W	IV	30
BMS-986226	PK/PD from Part C	TBD	IV	30

Table 7.1-1:Selection and Timing of Dose per Part

^a Weight collected at baseline/screening should be used to calculate ipilimumab dose unless weight has changes more than +/- 10% from baseline on C1D1

Note: In Parts B, C, D, and E a 30-minute infusion of either nivolumab or ipilimumab will be followed by a 30-minute observation period, followed by a 30-minute infusion of BMS-986226. In all parts, participants will be observed for at least 60 minutes following the completion of BMS-986226 infusion due to the potential risk of, and to monitor for, infusion reactions.

In order to reduce the risk of infusion-related reactions, participants enrolled in all study parts are recommended to receive premedication 30 minutes prior to initiation of study treatment. Recommended premedications include a H1 histamine antagonist, such as diphenhydramine 50 mg (or equivalent), and an antipyretic, such as acetaminophen/paracetamol 325 to 1000 mg (or equivalent). Premedication should be administered prior to infusion of any study drug, and should comply with the permitted medications and dosing described in Section 7.6. Any alternative premedication regimen must be discussed with, and approved by the BMS Medical Monitor/Study Director prior to administration of any study treatment. Medical management of any infusion reactions occurring irrespective of whether premedication was administered, remain at the discretion of the investigator. Guidelines for management of infusion reactions are described in Section 7.3.6.

7.1.1 Method of Treatment Assignment

This is an open-label study. All participants must be assigned a participant number upon providing signed written informed consent. Based on the rate of participant enrollment, the Sponsor will implement an IRT to assign participant numbers, study treatment group, and dose level, as well as manage drug supply. During the screening visit, the investigative site will register the participant by an IRT designated by BMS for assignment of a 5-digit participant number that will be unique across all sites. Enrolled participants, including those not dosed, will be assigned sequential participant numbers.

The participant identification number (PID) will ultimately be composed of the site number and participant number. For example, the first participant screened (e.g., enrolled) at site number 1, will have a PID **Example**. Specific instructions for using the IRT will be provided to the investigational sites in a separate instruction manual.

Once it is determined that the participant meets the eligibility criteria following the screening visit, the assigned treatment group and dose level will be provided to the site study team through the IRT prior to the first study treatment administration. The participant will be informed of one of the following:

- Assigned to a part (Preliminary Safety Cohorts and Part A) and dose cohort in the dose escalation portion of the study.
- Assigned to a part (Part B1, B2, C1, or C2) in the combination portion of the study.
- Assigned to the expansion portion of the study (Parts D and E)

During dose escalation, all participants will be assigned to the Preliminary Safety Cohorts, then Part A until the decision is made to start the combination with either nivolumab or ipilimumab. If there are no openings available in the part to which the participant would be assigned by this algorithm, then the participant will be assigned to the next open part/cohort. In the event that multiple cohorts are open in Parts B and/or C simultaneously, participants will be assigned to those cohorts in an alternating fashion.

During dose escalation (Preliminary Safety Cohorts and Part A), participants who are not evaluable for DLT determination may be replaced (see Section 5.1.2.1). Replacement participants will be assigned to the same part (Part A) and dose, but will be assigned a new participant number. Please refer to the IRT manual for complete details on replacement of participants.

Participants in Parts A, B and C may be replaced if adequate paired pretreatment and on-treatment biopsy specimens are not obtained. The replacement participant will receive the same treatment as that for the participant being replaced, but a new participant number will be assigned (see Section 5.1.2.2 and 5.1.2.3).

7.2 Blinding

This is a non-randomized, open-label study; blinding procedures are not applicable.

7.3 Dosage Modification

With the exclusion of the Preliminary Safety Cohorts, intra-participant dose escalation or reduction of BMS-986226, nivolumab, or ipilimumab is not permitted in this study in order to allow better evaluation of the safety and efficacy at individual dose levels and schedules.

7.3.1 Treatment Delay

Participants who experience a DLT must have the study treatment held. Participants who are required to permanently discontinue both study treatments are listed in Section 8.1. In addition, all Grade 2 hepatic, pulmonary, renal, GI, and neurological AEs should be evaluated and managed per the toxicity management algorithms (Appendix 6). Participants not meeting guidelines for

permanent discontinuation will be permitted to resume study treatment based on the criteria specified below in Section 8.1.1. Participants eligible to resume study treatment will resume study treatment at the visit following their last received dose.

In all cohorts, if there is a delay in dosing of BMS-986226 alone or in combination with nivolumab or ipilimumab, between 1 and 12 days, the procedures at the original scheduled visit should be performed as soon as possible. If the delay is more than 12 days, the visit and dose will be considered missed; the procedures at the next scheduled visit should be performed, and subsequent BMS-986226 doses will follow every 4 weeks.

Extensions to the period of dose delays may be granted for individual participants on a case-by-case basis after specific consultation and agreement between the investigator and BMS Medical Monitor/Study Director (or designee) in settings where benefit/risk may justify continued study treatment (eg, participant deriving clinical benefit who requires prolonged steroid taper for the management of non-DLT -drug-related- AEs or experiences delays for the management of a nondrug-related AE).

The end of cycle tumor assessments (ie, CT/MRI, PET, etc) will continue on a Q8W schedule relative to the participant's first dose regardless of any study treatment delay incurred.

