All Parts: BMS-986226 Administration	Х					Х				Use vials assigned per IRT. Safety Cohort and Part A BMS-986226 will be administered every 4 weeks on the first day of each cycle Parts B1 and C1: BMS-986226 will be administered on Day 1 every 12 weeks (Cycle 1 Day1, Cycle 4 Day1, Cycle 7 Day 1, etc) Parts B2 and C2: BMS-986226 will be administered every 4 weeks on the first day of each cycle Parts D and E: The dose and schedule of BMS-986226 will be determined based on available data from Parts A, B1, B2, C1 and C2.

Procedures for Safety Cohort, and Parts A, B, C, D and E ^{a,b}			C2 to beyond	C2 Only	C2 Only		Notes			
Procedure	D1	D2	D8 ± 1 days	D15 ±1 days	D22 ±1 days	D1	D2	D8 ±1 days	EOT c,d,e	
Parts B1, B2, and D ONLY: Nivolumab Administration	Х					Х				Use vials assigned per IRT. Nivolumab is administered ONLY for those participants enrolled in Parts B1, B2, and D.
Parts C1, C2, and E ONLY: Ipilimumab Administration	Х					X				Use vials assigned per IRT. Ipilimumab is administered ONLY for those participants enrolled in Parts C1, C2 and E.

^a The procedural outline for participants who receive additional cycles are outlined in Table 2-4.

^b Participants taking 2 or 8 mg of BMS-986226 in the Preliminary Safety Cohorts will follow the same procedure schedule as in Part A. In the event that participants taking 2 or 8 mg of BMS-986226 should be permitted to intra-dose escalate up to 8 and/or 25 mg, the sampling schedule should be restarted at Cycle 1 Day 1 at each dose escalation, and an additional tumor biopsy may be optionally re-collected at C1D15.

^c EOT is defined as the visit where a decision is made to discontinue the participant from treatment.

^d For participants who complete all scheduled cycles of therapy, the EOT visit will be the same as the last scheduled and completed on-treatment visit (eg, Cycle 6 Day 175) and the start of the Week 1 safety follow-up visit.

^e For participants who do not complete all scheduled cycles of therapy, the EOT visit will be the most recent on-treatment visit (with all available safety and response data) and does not need to be repeated, and it will be considered the start of the Week 1 safety follow-up visit.

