5 STUDY DESIGN

Figure 5-1: Study Design Schematic

* Note: Arms B2 and C2 will enroll only if additional safety, PK, and PD data are required to inform dose expansion decisions. The dose levels assessed in B2 and C2 will not exceed those evaluated in Part A, B1, or C1.

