5.1.2 Treatment Phase

The treatment phase in the Preliminary Safety Cohort and Part A consists of up to six 4-week treatment cycles (1 cycle = 28 days). In the Preliminary Safety Cohort and Part A, each treatment cycle will consist of BMS-986226 monotherapy for a total of 24 weeks.

Dose levels for Parts B and C will be determined based on all available safety (clinical and laboratory) and PK data, as well as changes in peripheral target engagement markers (eg, ICOS

downregulation on T cells and ICOS + B cells) from previous and completed portion of current cohorts, and will be guided by the BLRM/BLRM-Copula model whenever applicable.

In Parts B1 and C1, 4 week cycles will be used, such that BMS986226 + nivolumab or ipilimumab will be administered starting on Cycle 1 Day 1. Nivolumab and ipilimumab will be administered on Day 1 of each cycle. BMS-986226 will be administered Q12W, or on Day 1 of every third cycle (Cycle 1 Day1, Cycle 4, Day1, Cycle 7 Day1, etc.). Participants on Parts B1 and C1 may continue treatment for up to a total of 2 years.

The treatment phase in Parts B2 and C2 will consist of BMS-986226 + nivolumab or ipilimumab administered on Day 1 of each cycle and will be enrolled if additional safety, PK, or PD data is required to optimize dose and/or schedule selection. In parts B2 and C2 BMS-986226 will be administered Q4W and participants may continue treatment for a total of 2 years.

Following each treatment cycle, the decision to treat a participant with additional cycles of study treatment will be based on tumor assessment evaluations performed every 8 weeks $(Q8W \pm 1 \text{ week})$ and completed before the first dose in the next cycle. Tumor progression or response endpoints will be assessed using Response Evaluation Criteria In Solid Tumors (RECIST) v1.1 (Appendix 5) or PCWG3, for prostate only (Appendix 11).

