5.5 Justification for Dose and Schedules for BMS-986226, Nivolumab, and Ipilimumab

5.5.1 Rationale for BMS-986226 Flat Dosing and Schedule

Therapeutic mAb doses have been routinely calculated on a body size basis with a perception that this approach may reduce inter-participant variability in drug exposure compared with a flat dose approach. However, recent analyses of marketed experimental mAbs have demonstrated that body weight-based dosing did not always offer advantages over flat dosing in reducing exposure variability. Because the magnitude of the impact of body weight on the human PK of BMS-986226 is not yet determined and it is unknown if body size-based dosing would increase or decrease inter-participant variability, this study will utilize a flat dose in the escalation and combination phases as a more convenient approach and which is more likely to reduce the potential for dosing errors.

The starting dose of BMS-986226 in combination with either nivolumab 480 mg Q4W or ipilimumab 3 mg/kg Q4W will be determined based on the expected activity at this dose range and the expected tolerability and safety profile of BMS-986226 in the monotherapy dose escalation (Part A). At no point will the dose of BMS-986226 administered in combination with nivolumab or ipilimumab- exceed doses of BMS-986226 that have been demonstrated previously to be tolerated in the monotherapy dose escalation arm (Part A). Accordingly, additional intermediate

or lower doses or less frequent dosing of BMS-986226 may be tested, if none of the planned doses/schedule is found to be tolerated when combined with nivolumab or ipilimumab.

The BMS-986226 dose for Parts B and C will be based on evaluating the most up-to-date data available in all dosed participants, including clinical and laboratory safety assessments as well as PK, PD, and efficacy data from all treated participants at each dose level up to the MAD.

For the Preliminary Safety Cohorts and Parts A, B2 and C2, BMS-986226 will be administered at a dose schedule of Q4W. This schedule is based on predicted human PK using nonclinical data. The projected T-HALF for BMS-986226 in humans is 25 days (Section 3.2.2.5), allowing for dosing at an interval of 4 weeks.

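### The missed-dose rule in Section 7.3.1 sets later BMS-986226 doses at every 4 weeks in all cohorts, which is wrong for the Q12W Parts B1 and C1

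*Combined protocol and SAP*

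**What the plan says.** The delay rule in Section 7.3.1 opens with its scope: "In all cohorts, if there is a delay in dosing of BMS-986226 alone or in combination with nivolumab or ipilimumab". A delay of 1 to 12 days means that the visit is done as soon as possible. Beyond 12 days the visit and dose count as missed, and "the procedures at the next scheduled visit should be performed, and subsequent BMS-986226 doses will follow every 4 weeks". No part is excepted.

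The planned schedule for Parts B1 and C1 is different. Section 5.1.2 says "BMS-986226 will be administered Q12W, or on Day 1 of every third cycle", and Table 2-2 in Section 2 says "BMS-986226 will be administered on Day 1 every 12 weeks (Cycle 1 Day1, Cycle 4 Day1, Cycle 7 Day 1, etc". The synopsis, Section 5.1 and Table 7.1-1 agree. Section 5.5.1 lists the 4-weekly parts, and B1 and C1 are not among them: "For the Preliminary Safety Cohorts and Parts A, B2 and C2, BMS-986226 will be administered at a dose schedule of Q4W". The partner drug has its own calendar in these parts: "Nivolumab and ipilimumab will be administered on Day 1 of each cycle".

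On resumption, Section 7.3.1 says "Participants eligible to resume study treatment will resume study treatment at the visit following their last received dose". Sections 7.3.4 and 8.1.1 point to the nominal visit or the next nominally scheduled time point. Section 8.1 requires discontinuation when a delay exceeds 6 weeks from the previous dose. It excepts prolonged steroid tapers for treatment-related events and approved delays that are not drug-related. Section 8.1.1 repeats the 6-week limit.

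**The concern.** Section 7.3.1 is the only text that states the dosing interval after a missed dose, so a site would look there. Taken at its word, it moves a B1 or C1 participant to the interval that defines B2 or C2. The 12-week interval is the purpose of B1 and C1: they were set up to follow ICOS downregulation and re-expression under that spacing. Section 7.3 also bars dose changes within a participant outside the Preliminary Safety Cohorts, so that each dose level and schedule can be assessed separately.

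A participant switched in this way would contribute later safety and exposure data that no longer describe the assigned schedule, and the switch would fall only on people who had a delay. Opening of the 4-weekly combination parts is conditional: "Arms B2 and C2 will enroll only if additional safety, PK, and PD data are required to inform dose expansion decisions". Part A gives 4-weekly experience with BMS-986226 alone only. Some 4-weekly combination exposure could therefore occur at a dose level where B2 or C2 has not opened.

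**Working it through.** The plan gives no figure to reproduce here. The check compares the dosing intervals, asks who can reach the clause, and counts doses.

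**1. Inputs.** Cycles are 4 weeks, and B1/C1 treatment lasts up to 2 years (Section 5.1.2), taken as 104 weeks: 104 / 4 = 26 cycles. The Q12W calendar is cycles 1, 4, 7, ..., 25, which is 9 doses. The first dose that can be missed after starting is Cycle 4 Day 1 (C4D1), and the last is C25D1.

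**2. Interval.** Planned: 3 x 28 = 84 days. Section 7.3.1: 28 days. Ratio 84 / 28 = 3.

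**3. Who reaches the clause.** Suppose that the whole C4D1 visit is missed, partner drug included. The last study treatment was at C3D1. Restart at C5D1 is 2 x 4 = 8 weeks later, beyond the 6 weeks in Section 8.1, so the default is discontinuation. Two routes remain:
- one of the Section 8.1 exceptions applies (prolonged steroid taper, or an approved non-drug-related delay);
- BMS-986226 alone is missed and the partner drug is given on time. Section 8.1 assesses discontinuation separately for the two drugs.

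I count the 6 weeks from the last study treatment of either drug. Counted from the last BMS-986226 dose, the limit would be exceeded by the planned 12-week gap itself.

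**4. Dose counts for a participant who continues.** The restart is taken either as the next cycle visit or as the next Q12W visit. The comparator is the Q12W calendar kept, or Q12W counted afresh from the next cycle visit.

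| Case | Every 4 weeks from next cycle visit | Every 4 weeks from next Q12W visit | Q12W calendar kept | Q12W counted afresh |
|---|---|---|---|---|
| C4D1 missed, treated through cycle 26 | 1 + 22 = 23 | 1 + 20 = 21 | 1 + 7 = 8 | 1 + 8 = 9 |
| C4D1 missed, last cycle 13 | 1 + 9 = 10 | 1 + 7 = 8 | 4 | 4 |
| C4D1 missed, last cycle 6 | 1 + 2 = 3 | 1 | 1 | 2 |
| C25D1 missed, treated through cycle 26 | 8 + 1 = 9 | 8 | 8 | 9 |

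Excess over the calendar kept:
- through cycle 26: 21 - 8 = 13 to 23 - 8 = 15;
- last cycle 13: 8 - 4 = 4 to 10 - 4 = 6;
- last cycle 6: 1 - 1 = 0 to 3 - 1 = 2;
- C25D1 missed: 8 - 8 = 0 to 9 - 8 = 1.

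**5. What is out of reach.** The DLT period is 35 days, and the second B1/C1 dose is due 84 days after the first. The clause cannot act within the DLT window or the first 12-week interval. The detection probabilities in Section 10.1.2 depend only on the numbers treated.

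**6. Scale.** About 6 evaluable participants x up to 3 dose levels x 2 parts = about 36. One switched participant is 1/6 = 17% of a dose level. That is a proportion, not an expected effect, because the protocol gives no rate of missed doses.

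**The case against.** The best defence is that the rest of the protocol stops most of this. The 6-week rule removes by default anyone who misses a whole visit, and one of its exceptions needs sponsor approval. Section 7.3.1 refers resumption to Section 8.1.1, whose next nominal time point for BMS-986226 in B1/C1 can only sensibly be C4, C7, C10 and so on. Q12W is stated in many other places, vials are assigned through IRT, and the B1/C1 end-of-infusion samples are set at cycles 1, 4, 7 and 10. Literal use is therefore unlikely.

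Most of this stands, and it limits the point in four ways:
- A reader might infer that every B1/C1 participant with a missed dose moves to 4-weekly dosing. Section 8.1 does not support that.
- A reader might take 23 against 8 doses as typical. It needs the earliest possible miss, an escape from the 6-week rule, and treatment through cycle 26.
- A reader might see a second contradiction in the restart visit, because the partner drug brings participants in every 4 weeks. Section 8.1.1 does not name the drug, but it largely settles this in favour of the Q12W visit, so what remains is an ambiguity.
- A reader might infer that 4-weekly combination dosing would necessarily come before B2 or C2 opens. Those parts may enrol alongside B1/C1 and may open at a dose level after one B1/C1 participant has been treated there.

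The defence does not remove the conflict. None of these passages changes the interval that Section 7.3.1 sets, and the two routes in step 3 leave participants to whom it applies.

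**Conclusion.** The clause is wrong as written for Parts B1 and C1 and should be corrected. For a participant who continues after a missed dose, literal use triples the BMS-986226 dosing rate. The excess runs from 0 to 1 dose (last possible miss) or 0 to 2 (treatment ending at cycle 6), through 4 to 6 (ending at cycle 13), to an extreme of 13 to 15 (C4D1 missed, treated through cycle 26). How many participants would be affected cannot be estimated from the documents.

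This rests on three assumptions: 2 years means 26 cycles, the 6-week limit runs from the last study treatment of either drug, and every later dose is given at the interval in Section 7.3.1. The documents do not support a wider claim that dose-escalation decisions, the first-interval ICOS kinetics or the sample size are compromised.

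**What to change.** In Section 7.3.1, replace the 4-weekly clause with wording such as: *subsequent doses will follow the BMS-986226 schedule of the assigned part (Q4W, or Q12W in Parts B1 and C1)*. Referring to the assigned part also covers Parts D and E, whose schedule is still to be set.

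As a clarification, add that a missed Q12W dose resumes at the next nominal BMS-986226 visit, consistent with Section 8.1.1, while the partner drug continues every 4 weeks.

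The cost is one clause and one clarifying sentence in the next revision. It needs no extra participants, visits or procedures.
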